8.2.2. Dose-Limiting Toxicities

The participants with DLTs and the type of DLT will be listed by dose level.

8.2.3. Events of Clinical Interest

An ECI is an AE (serious or nonserious) that Incyte wishes to document in an organized manner for monitoring or understanding. An ECI does not require rapid communication by an investigator to Incyte unless it meets criteria for rapid communication as an SAE.

The following laboratory abnormalities and/or clinical AEs are considered ECIs:

- Tafasitamab:
 - Tumor lysis syndrome
 - IRRs
 - Allergic reactions to study drug \geq Grade 3
 - CRS
 - Secondary primary malignancy

- Hepatitis B reactivation
- Progressive multifocal leukoencephalopathy
- Parsaclisib
 - ALT $\geq 5 \times$ ULN
 - AST $\geq 5 \times$ ULN
 - Colitis
 - Diarrhea \geq Grade 3
 - Intestinal perforation
 - Rash \geq Grade 3
 - Exfoliative dermatitis
 - Pneumonitis
 - PJP infection
 - CMV infection
 - Herpes simplex virus infection
 - Varicella zoster virus infection

The number of participants who experienced the events of interest listed above will be summarized by maximum severity.

8.2.4. Adverse Event Summaries

An overall summary of AEs by cohort will include the following:

- Number (%) of participants who had any TEAEs
- Number (%) of participants who had any serious TEAEs
- Number (%) of participants who had any Grade 3 or higher TEAEs
- Number (%) of participants who had any fatal TEAEs
- Number (%) of participants who had a DLT
- Number (%) of participants who had any TEAEs related to tafasitamab
- Number (%) of participants who had any TEAEs related to parsaclisib
- Number (%) of participants who interrupted tafasitamab because of TEAEs
- Number (%) of participants who interrupted parsaclisib because of TEAEs
- Number (%) of participants who permanently discontinued tafasitamab because of TEAEs
- Number (%) of participants who permanently discontinued parsaclisib because of TEAEs

- Number (%) of participants who had tafasitamab dose reductions because of TEAEs
- Number (%) of participants who had parsaclisib dose reductions because of TEAEs
- Number (%) of participants who withdrew from the study because of TEAEs

The following summaries will be produced by MedDRA term (if 10 or fewer participants appear in a table, a listing may be appropriate):

- Summary of TEAEs by MedDRA SOC and PT
- Summary of TEAEs by MedDRA PT in decreasing order of frequency
- Summary of TEAEs by MedDRA SOC, PT, and maximum severity
- Summary of Grade 3 or higher TEAEs by MedDRA SOC and PT
- Summary of Grade 3 or higher TEAEs by MedDRA PT in decreasing order of frequency
- Summary of serious TEAEs by MedDRA SOC and PT
- Summary of serious TEAEs by MedDRA PT in decreasing order of frequency
- Summary of tafasitamab treatment-related TEAEs by MedDRA SOC and PT
- Summary of parsaclisib treatment-related TEAEs by MedDRA SOC and PT
- Summary of tafasitamab treatment-related TEAEs by MedDRA PT in decreasing order of frequency
- Summary of parsaclisib treatment-related TEAEs by MedDRA PT in decreasing order of frequency
- Summary of tafasitamab treatment-related TEAEs by MedDRA SOC, PT, and maximum severity
- Summary of parsaclisib treatment-related TEAEs by MedDRA SOC, PT, and maximum severity
- Summary of Grade 3 or higher tafasitamab treatment-related TEAEs by MedDRA SOC and PT
- Summary of Grade 3 or higher parsaclisib treatment-related TEAEs by MedDRA SOC and PT
- Summary of tafasitamab treatment-related serious TEAEs by MedDRA SOC and PT
- Summary of parsaclisib treatment-related serious TEAEs by MedDRA SOC and PT
- Summary of TEAEs with a fatal outcome by MedDRA SOC and PT
- Summary of TEAEs leading to dose reduction by MedDRA SOC and PT
- Summary of TEAEs leading to dose interruption by MedDRA SOC and PT
- Summary of TEAEs leading to discontinuation of study drugs by MedDRA SOC and PT

- Summary of TEAEs of tafasitamab ECI by ECI class, PT, and maximum severity
- Summary of TEAEs of parsaclisib ECI by ECI class, PT, and maximum severity
- Summary of Dose-Limiting Toxicities

8.3. Clinical Laboratory Tests

8.3.1. Laboratory Value Definitions

Laboratory values and change from baseline values will be summarized descriptively by visit. Baseline will be determined according to Section 4.1.3. If there are multiple values that meet the criteria for baseline, additional rules may be provided after consultation with the medical monitor to delineate which value will be defined as baseline.

Laboratory test values will be assessed for severity based on the numerical component of CTCAE v5.0.

8.3.2. Laboratory Value Summaries

All laboratory test results and associated normal ranges from local laboratories will be reported in SI units. Any laboratory test results and associated normal ranges from local laboratories will be converted to SI units. When there are multiple nonmissing laboratory values for a participant's particular test at a scheduled visit, the laboratory value with the smallest laboratory sequence number will be used in by-visit summaries.

Numeric laboratory values will be summarized descriptively in SI units, and non-numeric test values will be tabulated when necessary. In addition, line graphs will be provided for hemoglobin, platelet counts, circulating lymphocyte counts, and neutrophils.

Severity grades will be assigned to laboratory test values based on the numerical component of CTCAE v5.0. Shift tables will be presented showing change in CTCAE grade from baseline to worst grade postbaseline. Separate summaries for abnormally high and abnormally low laboratory values will be provided when the laboratory parameter has both high and low grading criteria. The denominator for the percentage calculation will be the number of participants in the baseline category. The number of participants who experienced worsening of laboratory abnormalities will be summarized by maximum severity.

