**Table 3: Schedule of Activities (Continued)**

Visit Day (Range)	Screening	Treatment						EOT	Follow-up			Notes
		Cycles 1-3			Cycle 4 Onward				Safety	Disease	Survival	
	Days -28 to -1	Day 1	Day 8 (± 1 d)	Day 15 (± 1 d)	Day 22 (± 1 d)	Day 1 (± 1 d)	Day 15 (± 1 d)		EOT + 90 d	Post- Treatment	Last Visit + 12 Wk (± 7 d)	
Urinalysis	X							X				
Coagulation	X							X				
Lipid panel	X							X				
Endocrine function	X							X				

EDTA = ethylenediaminetetraacetic acid.

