## **8.8. Follow-Up**

### **8.8.1. Safety Follow-Up**

The safety follow-up period is the interval between the EOT visit and the scheduled follow-up visit, which should occur 90 days after the EOT visit (or after the last dose of study treatment if the EOT visit was not performed). Adverse events and SAEs must be reported up until 1) at least 90 days after EOT/last dose of study treatment or the start of a new anticancer therapy or 2) until toxicities resolve, return to baseline, or are deemed irreversible, whichever is longer. Reasonable efforts should be made to have the participant return for the follow-up visit and report any AEs that may occur during this period.

If a participant is scheduled to begin a new anticancer therapy before the end of the safety follow-up period, the safety follow-up visit should be performed before a new anticancer therapy is started. Once a new anticancer therapy has been initiated, the participant will move into the survival follow-up period.

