5.3.2. Full Analysis Set

The FAS will include all participants who received at least 1 dose of tafasitamab or parsaclisib. The FAS will be used for the summary of demographics, baseline characteristics, participant disposition, and analyses of all safety and efficacy data.

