6.2. Disposition of Participant

The number and percentage of participants who were treated, who were ongoing with study treatment, who discontinued study treatment with a primary reason for discontinuation, who were still in the study, who completed the study, and who withdrew from the study with a primary reason for withdrawal will be summarized for the FAS. The number of participants enrolled by country and/or site will also be provided for the FAS.

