3.3 Laboratory			
3.3.1.1	Summary of Laboratory Values – Hematology	FAS	X
3.3.1.2	Summary of Laboratory Values – Chemistry	FAS	X
3.3.1.3	Summary of Laboratory Values – Coagulation	FAS	X
3.3.1.4	Summary of Laboratory Values – Urinalysis	FAS	X
3.3.3.1	Shift Summary of Hematology Laboratory Values in CTCAE Grade – to the Worst Abnormal Value	FAS	X
3.3.3.2	Shift Summary of Chemistry Laboratory Values in CTCAE Grade – to the Worst Abnormal Value	FAS	X
3.3.3.3	Shift Summary of Coagulation Laboratory Values in CTCAE Grade – to the Worst Abnormal Value	FAS	X
3.3.3.4	Treatment-Emergent Worsening of Laboratory Abnormalities – Hematology	FAS	X
3.3.3.5	Treatment-Emergent Worsening of Laboratory Abnormalities – Chemistry	FAS	X
3.3.3.6	Treatment-Emergent Worsening of Laboratory Abnormalities – Coagulation	FAS	X

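### The shift-table denominator in SAP 8.3.2 keeps participants with no postbaseline value, which dilutes the coagulation percentages because coagulation is scheduled again only at end of treatment

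*SAP*

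**What the plan says.** SAP 8.3.2 describes the table as follows: "Shift tables will be presented showing change in CTCAE grade from baseline to worst grade postbaseline". For the percentages it adds: "The denominator for the percentage calculation will be the number of participants in the baseline category". It names no category for participants without a postbaseline value and does not condition the denominator on having one.

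SAP Appendix A plans a coagulation version in the full analysis set (FAS), Table 3.3.3.3: "Shift Summary of Coagulation Laboratory Values in CTCAE Grade – to the Worst Abnormal Value". The FAS itself requires no laboratory follow-up: "The FAS will include all participants who received at least 1 dose of tafasitamab or parsaclisib" (SAP 5.3.2).

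In the protocol's Table 3, the coagulation row is marked at screening and at EOT, with nothing in Cycles 1 to 3, from Cycle 4 onward, or in follow-up. Hematology and serum chemistry are marked at every treatment visit.

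Both documents provide for participants without an EOT sample. Protocol 8.8.1 times the safety follow-up visit from EOT, "or after the last dose of study treatment if the EOT visit was not performed". SAP 6.2 counts in the disposition summary participants "who were ongoing with study treatment", who have not yet reached EOT.

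**The concern.** The numerator of a worsened cell needs a postbaseline grade; the denominator does not. For a test repeated at every visit the mismatch hardly matters, because almost every treated participant will have a later value. For a test scheduled once after baseline, at the end of treatment, it can matter.

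The direction is the less cautious one for safety, since missing samples lower the reported percentage. Participants who die on treatment or stop abruptly are plausibly among those without an EOT sample, so the missing values need not resemble the observed ones. Tables 3.3.3.1 to 3.3.3.3 would also look alike and use one percentage rule while resting on very different completeness.

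**Working it through.** The plan gives no coagulation worsening rate and no expected share of missing EOT samples, so there is no figure of its own to reproduce.

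**Inputs**
- B: participants in one baseline grade (the SAP 8.3.2 denominator).
- u: those among B with no postbaseline coagulation value. Not in the documents; assumed.
- w: those among B whose worst postbaseline grade is higher than baseline. Assumed.
- m = u/B.

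**Formulas**
- Percentage under SAP 8.3.2 = w/B.
- Percentage among assessed = w/(B - u).
- Ratio of the first to the second = (B - u)/B = 1 - m, so the relative reduction equals m.
- Highest rate compatible with the data, if every untested participant had worsened = (w + u)/B.

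**Numbers.** Take B = 20, the planned maximum of evaluable participants per cohort (SAP 3.3), and w = 4. This assumes that all 20 share one baseline grade, because the denominator is the grade and not the cohort.

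| u | m | SAP 8.3.2 | Among assessed | Ratio | If all untested worsened |
|---|---|---|---|---|---|
| 0 | 0% | 4/20 = 20.0% | 4/20 = 20.0% | 1.00 | 20.0% |
| 2 | 10% | 20.0% | 4/18 = 22.2% | 0.90 | 6/20 = 30.0% |
| 4 | 20% | 20.0% | 4/16 = 25.0% | 0.80 | 8/20 = 40.0% |
| 6 | 30% | 20.0% | 4/14 = 28.6% | 0.70 | 10/20 = 50.0% |
| 8 | 40% | 20.0% | 4/12 = 33.3% | 0.60 | 12/20 = 60.0% |

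The SAP percentage stays at 20.0% however many samples are missing. It is the lowest rate compatible with the data, reached only if no untested participant worsened.

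**Which tables are affected.** Appendix A plans shift tables for hematology, chemistry and coagulation. Of these, only coagulation is scheduled at EOT alone after baseline. Table 3.3.3.6 summarises coagulation worsening. For worsening summaries SAP 8.3.2 promises a number of participants by maximum severity and states no denominator, so any percentage added there would face the same choice.

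**The case against.** The strongest reply is that the SAP nowhere classes untested participants as not worsened. A reader might infer that from the denominator rule, but the text does not say it; it is only what the division does to the percentage. The table shells are in a separate document and may already carry a missing column. That stands. Such a column would expose the gap, but under the stated rule the percentages beside it would still be diluted.

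Second, testing after baseline is not strictly confined to EOT. Protocol 8.3.8 allows additional tests when clinically indicated, and abnormalities that are clinically meaningful are reported as adverse events (Protocol 9.1). This also stands: some participants will have an unscheduled value, and a serious coagulation problem has another route into the safety tables.

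Third, the amount missing is unknown. Protocol 8.8.1 is a fallback for timing a visit, not a forecast that EOT visits will be missed, and Protocol 7.1.2 and 8.7 say the visit should take place. The tables are for the Clinical Study Report and no interim analysis is planned, so a cut with many participants still on treatment is possible but not foretold. A reader might infer a demonstrated bias of known size; the documents do not support that.

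Fourth, a reader might take the assessed-only rate as the true rate. It is not. If samples are missing for reasons related to outcome, or if those with EOT samples are mainly those who stopped early, that rate is selected too. This does not rescue the present rule, but it does mean that changing the denominator alone is not enough.

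Finally, the by-visit coagulation summary (Table 3.3.1.3) should give the number of observations at EOT, so overall missingness can be roughly recovered. It will not be broken down by baseline grade, and Appendix A lists no coagulation listing from which to rebuild it.

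**Conclusion.** The point holds as a narrow reporting issue. Under the rule as written, each percentage in a worsened cell of Table 3.3.3.3 equals the rate among assessed participants times (1 - m). The relative reduction is 10% to 40% for an assumed m of 10% to 40%, and zero if every participant in the grade has a postbaseline value. The 20% against 25% illustration rests on three assumptions: 20 participants in one baseline grade, 4 of them untested, and 4 worsened.

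The effect does not extend to hematology and chemistry in any important degree. Nor does it touch the objective response rate, the dose-limiting toxicity assessment, the sample size or any decision to open an expansion cohort. All analyses are declared exploratory, and this one is descriptive. It merits correction because the rule is explicit, works against caution in a safety table, and is cheap to change.

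**What to change.** In SAP 8.3.2, define the shift-table denominator as the participants in the baseline category who have at least one postbaseline value for that test, scheduled or unscheduled. In Tables 3.3.3.1 to 3.3.3.3, give the number in each baseline category without a postbaseline value its own column. Apply the same denominator to any percentages shown in Table 3.3.3.6.

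The two parts belong together. Because the assessed-only rate is open to selection when samples are not missing at random, the missing count must stand beside it so that the reader can see how much of the category it describes.

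The cost is one sentence in the SAP and one column in the shells, if it is not there already. No new data or visits are needed.

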8.3.3. Potential Hy's Law Events

Participants with elevated ALT or AST $> 3 \times$ ULN range and alkaline phosphatase $< 2 \times$ ULN range accompanied by total bilirubin $> 2 \times$ ULN range at the same visit will be listed by treatment group.

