  - b. Progressive: PD after response of PR or stable disease to prior therapy.
  - c. Refractory: achieved less than PR to the last prior therapy, or achieved a CR or PR that lasted < 6 months before PD.
7. For Cohorts 1 to 4 and Cohort 5/SLL: radiographically measurable lymphadenopathy or extranodal lymphoid malignancy (defined as the presence of  $\geq 1$  lesion that measures  $> 1.5$  cm in the longest transverse diameter and  $\geq 1.0$  cm in the longest perpendicular diameter as assessed by CT or MRI).
8. ECOG performance status of 0 to 2.
9. Life expectancy  $> 3$  months.
10. LVEF  $\geq 50\%$ .
11. Laboratory results at screening as follows:
  - a. Hemoglobin level  $\geq 8$  g/dL (unless secondary to bone marrow involvement by NHL/CLL, as demonstrated by recent bone marrow aspiration and bone marrow biopsy).
  - b. ANC  $\geq 1.5 \times 10^9/L$  (unless secondary to bone marrow involvement by NHL/CLL, as demonstrated by recent bone marrow aspiration and bone marrow biopsy).
  - c. Platelet count  $\geq 75 \times 10^9/L$  (unless secondary to bone marrow involvement by NHL/CLL, as demonstrated by recent bone marrow aspiration and bone marrow biopsy).
  - d. Total serum bilirubin level  $\leq 1.5 \times$  ULN, or  $\leq 5 \times$  ULN in cases of Gilbert syndrome or documented liver involvement by lymphoma.
  - e. ALT, AST, and alkaline phosphatase level  $\leq 3 \times$  ULN, or  $\leq 5 \times$  ULN in cases of documented liver involvement.
  - f. Serum creatinine clearance  $\geq 50$  mL/min either measured or calculated using a standard Cockcroft and Gault formula ([Cockcroft and Gault 1976](#)).
12. Willingness to avoid pregnancy or fathering children based on the following criteria.
  - a. Male participants with childbearing potential must agree to take appropriate precautions to avoid fathering children (with at least 99% certainty) from screening through 6 months after the last dose of study treatment and must refrain from donating sperm during this period. Permitted methods that are at least 99% effective in preventing pregnancy (see [Appendix A](#)) should be communicated to the participants and their understanding confirmed.

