**Table 7: Definition of Dose-Limiting Toxicity**

Toxicity	Definition
Nonhematologic	

• Any liver function abnormalities that meet the definition of Hy's lawa.

• <math>\geq</math> Grade 4 tumor lysis syndrome or Grade 3 tumor lysis syndrome requiring dialysis.

• <math>\geq</math> Grade 4 fatigue lasting for <math>\geq</math> 7 days.

• <math>\geq</math> Grade 4 IRR.

• <math>\geq</math> Grade 3 CRS.

• Any other <math>\geq</math> Grade 3 nonhematologic toxicity except nausea, vomiting, electrolyte abnormality, or liver function abnormality

Hematologic	

• <math>\geq</math> Grade 3 hematologic toxicities lasting for <math>> 3</math> days excluding neutropenia and lymphocytopenia (also excluding thrombocytopenia in Groups 3 and 5).

• Grade 4 neutropenia (<math>ANC < 0.5 \times 10^9/L</math>) lasting for <math>\geq</math> 7 days in participants with pretreatment <math>ANC > 1 \times 10^9/L</math> under appropriate use of G-CSF (if G-CSF is required to manage neutropenia, the neutropenia is considered a DLT in Cohorts 1 and 2).

• Grade <math>\geq 4</math> thrombocytopenia in Cohorts 3 and 5.

• Febrile neutropenia.

General	

• Any death not clearly due to the underlying disease or extraneous causes.

• Any toxicity other than described above that (in the opinion of the investigator) is potentially life-threatening and cannot be controlled with standard measures.

• Any other toxicity that a primary investigator and the sponsor agree on being reported as a DLT.

a Hy's law is defined as 1) ALT or AST elevation  $> 3 \times ULN$ , 2) total bilirubin  $> 2 \times ULN$  without initial findings of cholestasis (elevated serum alkaline phosphatase), and 3) no other apparent possible causes of aminotransferase elevation and hyperbilirubinemia, including but not limited to viral hepatitis, pre-existing chronic or acute liver disease, or the administration of other drug(s) known to be hepatotoxic.

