#### Potential Hy's Law

An increase in AST or ALT  $> 3 \times$  ULN and total bilirubin  $> 2 \times$  ULN at any point during the study. The elevations do not have to be at the same time or within a specified timeframe.

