#### Hy's Law

An increase in AST or ALT  $\geq 3 \times$  ULN and total bilirubin  $> 2 \times$  ULN, where no other reason can be found to explain the combination of increases (eg, elevated serum ALP indicating cholestasis, viral hepatitis, another drug).

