### **ACTIONS REQUIRED IN CASES OF AST OR ALT $> 3 \times$ ULN OR TOTAL BILIRUBIN $\geq 2 \times$ ULN**

#### **Identification and Determination of Potential Hy's Law**

To identify cases of AST or ALT  $> 3 \times$  ULN or total bilirubin  $> 2 \times$  ULN and consequently determine whether the participant meets PHL criteria, please follow the instructions below:

- Review the laboratory report and if a participant has AST or ALT  $> 3 \times$  ULN OR total bilirubin  $> 2 \times$  ULN at any visit:
  - Determine without delay whether the participant meets PHL criteria by reviewing laboratory reports from all previous visits.
  - Enter the laboratory data into the laboratory eCRF as soon as possible.

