## Potential Hy's Law Criteria Met

If the participant has had AST or ALT  $\geq 3 \times$  ULN AND total bilirubin  $> 2 \times$  ULN at any point in the study (the elevations do not have to be at the same time or within a specified timeframe), irrespective of ALP, please follow the instruction below:

- Have participant interrupt study drug.
- Notify Incyte study team without delay.
  - The investigator, or designee, should contact the medical monitor to discuss and agree upon an approach for the study participant's follow-up and the continuous review of data.
- Monitor the participant until liver biochemistry parameters and appropriate clinical symptoms and signs return to normal or baseline levels, or as medically indicated.
- Investigate the etiology of the event and perform any relevant diagnostic investigations as discussed with the medical monitor.
- Enter the laboratory data into the laboratory CRF as soon as possible.
- If at any time (in consultation with the medical monitor) the PHL case meets serious criteria, report it as an SAE using standard reporting procedures.

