10.1. Changes to Protocol-Defined Analyses

A DLT evaluable population was added for analyzing results from the dose confirmation part of the study.

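### The SAP's Potential Hy's Law listing uses a narrower rule than Protocol Appendix G, so it will omit some protocol-defined cases

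*SAP*

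**What the plan says.** SAP 8.3.3 (Potential Hy's Law Events) sets three biochemical criteria: ALT or AST above 3 × ULN, ALP below 2 × ULN, and total bilirubin above 2 × ULN. It ties them to one visit: participants meeting them with bilirubin above the stated multiple of the "ULN range at the same visit will be listed by treatment group". The output is Listing 2.8.4 in SAP Appendix A, under the same name.

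Protocol Appendix G defines Potential Hy's Law differently.

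- **Timing.** The definition says: "The elevations do not have to be at the same time or within a specified timeframe".
- **Look-back.** When either value is raised, the site is told: "Determine without delay whether the participant meets PHL criteria by reviewing laboratory reports from all previous visits".
- **ALP.** The step for criteria that are met applies "irrespective of ALP, please follow the instruction below". The step for criteria that are not met has the same ALP wording.

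ALP enters Appendix G later, under Hy's Law itself, which covers cases "where no other reason can be found to explain the combination of increases". Raised ALP suggesting cholestasis is one example of such a reason. Footnote a of Protocol Table 7, on Hy's law as a DLT, similarly asks for bilirubin elevation "without initial findings of cholestasis (elevated serum alkaline phosphatase").

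SAP 10.1 declares one departure from the protocol: "A DLT evaluable population was added for analyzing results from the dose confirmation part of the study". SAP 2.1 keeps the SAP in force for later protocol amendments.

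**The concern.** One name carries two definitions, and the one used for reporting adds two conditions that the protocol explicitly sets aside. If the SAP is programmed as written, Listing 2.8.4 is not the set of Potential Hy's Law cases as the protocol defines them, although its title says it is.

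The Phase 1b primary objective is safety and tolerability, and liver enzyme elevations are already events of clinical interest for parsaclisib. A reader of the study report who looks for Potential Hy's Law cases will go to the listing with that title. A participant whose drug was interrupted and whose case was reviewed under Appendix G could be missing from it.

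The timing condition is the more serious of the two. The ALP condition at least resembles the later Hy's Law step. A same-visit requirement appears in neither the Hy's Law definition nor the DLT footnote.

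**Working it through.** There is no stated figure to reproduce, because the question is whether two logical rules select the same participants. All values below are multiples of ULN.

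**Rules**

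- SAP 8.3.3: some visit has (ALT or AST > 3) and (bilirubin > 2) and (ALP < 2).
- Appendix G, definition: some visit has (ALT or AST > 3), and some visit, the same or another, has (bilirubin > 2).
- Appendix G, criteria-met step: as the definition, but with ALT or AST ≥ 3.

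**Step 1: is the SAP set contained in the protocol set?** Yes. A visit that satisfies the SAP rule supplies both elevations that Appendix G needs.

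**Step 2: is it strictly smaller?** Take two visits, each with ALT 1 or 4, bilirubin 1 or 3, and ALP 1 or 2.5. That gives 8 states per visit and 8 × 8 = 64 patterns.

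- Protocol-positive: ALT raised at least once (3 of 4 arrangements) × bilirubin raised at least once (3 of 4) × any ALP (4) = 36.
- SAP-positive: one of the 8 states qualifies at each visit, so 64 − 7 × 7 = 15. All 15 are among the 36.
- Omitted: 36 − 15 = 21.
- Omitted because of timing: the two elevations fall at different visits only, 2 arrangements × 4 ALP combinations = 8.
- Omitted because of ALP: the elevations coincide at least once in 64 − 6 × 6 = 28 patterns, of which the SAP takes 15, leaving 28 − 15 = 13.
- Check: 8 + 13 = 21.

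The patterns are not equally likely in patients, so these counts show the logic and are not expected frequencies.

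**Step 3: constructed cases**, each visit shown as (ALT, bilirubin, ALP)

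| Case | Visits | SAP 8.3.3 | App. G definition (> 3) | App. G criteria-met step (≥ 3) |
|---|---|---|---|---|
| A | (6.0, 1.2, 1) (4.0, 2.4, 1) (2.5, 3.0, 1) | listed | counts | counts |
| B | (6.0, 1.2, 1) (3.4, 1.8, 1) (2.8, 2.4, 1) | omitted | counts | counts |
| C | (6.0, 2.6, 2.5) | omitted | counts | counts |
| D | (3.0, 2.6, 1) | omitted | does not count | counts |

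A is the control: bilirubin peaks late, but the two elevations overlap at one visit, so all the rules agree. B isolates the timing condition and C the ALP condition. D shows that Appendix G is itself inconsistent: the definition and the identification step use > 3, while the Hy's Law definition and the two criteria steps use ≥ 3. B and C are omitted under either reading.

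**Step 4: can these patterns arise here?** Protocol Table 3 schedules chemistry on Days 1, 8, 15 and 22 of Cycles 1–3 and on Days 1 and 15 thereafter, so a falling ALT and a rising bilirubin can be recorded at successive visits. Inclusion criterion 11e limits "ALT, AST, and alkaline phosphatase level" to 3 × ULN, or 5 × ULN with documented liver involvement. A participant may therefore enter with ALP already at 2 × ULN or more. If it stays there, that participant can never be listed, however high ALT and bilirubin rise. This applies to ALP only: the ALT of 6.0 in case C exceeds the entry limit and would have to develop on study.

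**The case against.** The strongest reply has four parts.

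1. **Appendix G governs site management, not analysis.** It limits its definitions to its own process, and Protocol Section 10 specifies no Potential Hy's Law analysis. A sensitive site trigger and a narrower reporting screen could coexist. This stands in part: the silence of SAP 10.1 is supporting evidence and not a breach in itself. It does not explain why the narrower screen carries the protocol's defined term.

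2. **The ALP condition has a clinical basis.** The Hy's Law definition and the DLT footnote both treat raised ALP as pointing elsewhere. That is true, but neither sets a 2 × ULN cut-off, neither requires a shared visit, and Appendix G keeps ALP out of the Potential Hy's Law step.

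3. **Omitted cases surface elsewhere.** ALT or AST ≥ 5 × ULN is a parsaclisib event of clinical interest (SAP 8.2.3; Table 3.2.21.2, Listing 2.7.8), so B and C would appear there. Confirmed Hy's Law, and cases still unresolved after 3 weeks, are reported as SAEs. This narrows the gap but does not close it. Take ALT 4.0 at one visit and, a week later, bilirubin 2.4 with ALT back below 3. That is Potential Hy's Law under the protocol, falls below the event-of-interest threshold, and is not in Listing 2.8.4. If review agrees a benign explanation that is not an AE, Appendix G asks only that it be recorded on a CRF where possible. The raw chemistry listings show the values but do not identify the case.

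4. **A footnote in the table shells may state the criteria.** The shells are a separate document and cannot be checked. A footnote would disclose the narrower rule but would not restore the missing cases.

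**Conclusion.** The concern holds. SAP 8.3.3 selects a strict subset of the participants whom Protocol Appendix G calls Potential Hy's Law, and it omits two kinds of case: elevations that never share a visit, and elevations that coincide only when ALP is 2 × ULN or higher. The conclusion follows from the current wording of both documents and needs no assumption about event rates. The number of cases affected cannot be derived from the documents, and none is claimed.

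The consequence is limited to the completeness of one safety listing. Drug interruption and case review at sites follow Appendix G. DLTs and SAEs have their own outputs, and the TEAE and DLT endpoints do not depend on Listing 2.8.4. The values remain in Listings 2.8.1.2 and 2.8.1.2.1. The change should be made before the listing is programmed, because it is the only planned output named for this event and it is cheap to correct.

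**What to change.** Replace the rule in SAP 8.3.3 with:

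> Listing 2.8.4 will include every participant with any post-baseline ALT or AST ≥ 3 × ULN and any post-baseline total bilirubin > 2 × ULN, at the same or different visits and regardless of ALP. It will show baseline ALT, AST, total bilirubin and ALP, on-study ALP, and the date of each elevation. Participants with ALT or AST > 3 × ULN, bilirubin > 2 × ULN and ALP < 2 × ULN at one visit will be flagged.

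Two choices should be stated openly in the SAP.

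- **The ≥ 3 threshold** is the one at which Appendix G interrupts study drug. It settles the appendix's mixed use of > 3 and ≥ 3 on the inclusive side.
- **The post-baseline limit** is slightly narrower than the appendix's whole-study wording. It keeps the listing to on-treatment findings, and the baseline columns show what was present at entry.

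The cost is one SAP sentence and a small programming change. More participants will be listed, including some with cholestasis and some who entered with raised values: criteria 11d and 11e allow bilirubin up to 5 × ULN in Gilbert syndrome or liver involvement, and ALT or AST up to 3 × ULN (5 × ULN with liver involvement). The baseline columns let a reader separate these, and the flag preserves the view the SAP now gives.

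If the sponsor prefers the narrower rule, the minimum is to rename the listing, print its criteria on it, and state the difference from Appendix G in SAP 10.1.
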